## 10.8 Sample size calculation

The sample size was chosen by the usual criteria of obtaining adequate power for the alternative hypothesis of interest as shown in [Table 4.2.1](#) and [Table 4.2.2](#) of [Appendix R](#). This hypothesis corresponds to a generally effective treatment across groups and incorporates variation in treatment effects to reflect the realistic expectation that treatment effects may differ by group. In this setting, analytical power calculations are not possible, but the design was simulated to obtain the power of the study as shown in the appendix. The sample sizes shown (minimum of 10 for futility stopping, minimum of 15 for early success and maximum of 30 as a group cap) achieve adequate power for the alternative hypothesis. The simulations

included the expected variable accrual by simulating a Poisson process with expected accrual also shown in the appendix.

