#### 10.4.2 Statistical hypothesis, model, and method of analysis

The study will enroll patients from at least 8 tumor cohorts, with each tumor cohort containing possible tumors of interest as shown in [Appendix R](#).

We let  $Y_i$  be the response indicator for the  $i^{\text{th}}$  subject, and let  $R_g$  be the assumed probability of response within a control population and  $\pi_g = \Pr(Y_i = 1 \mid g_i = g)$  be the underlying probability of response for group  $g$  within the trial. We transform to the logit scale for modeling purposes. Let  $\theta_g$  be the mean log odds treatment effect, i.e.:

$$\theta_g = \log\left(\frac{\pi_g}{1 - \pi_g}\right) - \log\left(\frac{R_g}{1 - R_g}\right)$$

Thus,  $\theta_g$  is the group specific logistic regression coefficient for group  $g$ . The primary analysis is a set of group specific tests that  $\theta_g > 0$ , meaning that the treatment is better than the assumed control rate for that group. Thus, we wish to test the set of hypotheses

$$H_{0g} : \theta_g \leq 0$$

$$H_{1g} : \theta_g > 0$$

We proceed in a Bayesian fashion, assigning a prior distribution (discussed below) and computing the posterior probability of  $H_{1g}$  within each group  $g$ . If, at the final analysis,

$$\Pr(\theta_g > 0 \mid \text{data}) > 0.80$$

Then group  $g$  will be declared a success (thus, the final analysis produces a separate decision for each group). The trial also allows for early stopping of groups..

The statistical design borrows information across groups with a hierarchical model. The hierarchical model allows dynamic borrowing of information between groups such that more borrowing occurs when the groups are consistent and less borrowing occurs when the groups differ. In this way, the model is a compromise between the two alternate extremes of either a completely pooled analysis or a separate analysis in each group. We additionally incorporate a clustering mechanism that allows borrowing within clusters but treats clusters separately. This minimizes borrowing across groups that are quite different in terms of CBR.

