**Table 4.1.1 Assumed control rates**

Tumor Type	Assumed Control Rate ( $R_g$ )
Lung NSC	0.45
Bladder	0.47
Breast	0.50
Colorectal	0.38
GIST	0.50
HNSCC	0.45
Ovarian	0.47
Sarcoma	0.40

Table 4.1.1 – Assumed control CBR values used in the simulations.

We consider four possible scenarios, or possible “truths” in the simulation. These consisted of a null scenario (where the treatment has no effect for any group), an alternative scenario (where the treatment is effective in all groups), a scenario where the treatment was effective in two of the groups, and a scenario where the treatment was effective in half of the groups.

Treatment Rates - The treatment rates for each scenario are shown in the [Table 4.1.2](#). Values identical to the control are shown in bold, while values greater than the assumed control rate are italicized.

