**Table 4.1.2 Treatment rates**

	Null	Alternative	Two	Half
Lung NSC	0.45	0.71	0.45	0.45
Bladder	0.47	0.73	0.47	0.47
Breast	0.50	0.75	0.50	0.50
Colorectal	0.38	0.65	0.38	0.38
GIST	0.50	0.75	0.50	0.75
HNSCC	0.45	0.71	0.45	0.71
Ovarian	0.47	0.73	0.73	0.73
Sarcoma	0.40	0.67	0.67	0.67

Simulation Details – For each scenario we simulated 1000 trials. For each interim within each trial, we ran 50,000 MCMC iterations after a 1,000 MCMC iteration burnin.

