**Table 4.2.1 Probability of group success for each cohort assuming expected accrual of 10 subjects/cohort**

Two-year expected accrual: 10 subjects/cohort				
Group(Exp N)	Null	Alternative	Two	Half
Lung NSC	0.158	0.915	0.208	0.305
Bladder	0.131	0.918	0.232	0.322
Breast	0.147	0.909	0.233	0.312
Colorectal	0.138	0.921	0.200	0.276
GIST	0.162	0.921	0.233	0.826
HNSCC	0.139	0.906	0.217	0.834
Ovarian	0.145	0.929	0.786	0.829
Sarcoma	0.135	0.939	0.758	0.852

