**Table 4.2.2 Probability of group success for each cohort assuming expected accrual of 5 subjects /cohort**

Two-year expected accrual: 5 subjects/cohort				
Group	Null	Alternative	Two	Half
Lung NSC	0.132	0.803	0.204	0.258
Bladder	0.140	0.830	0.196	0.265
Breast	0.160	0.807	0.232	0.261
Colorectal	0.135	0.794	0.194	0.278
GIST	0.155	0.826	0.212	0.688
HNSCC	0.140	0.820	0.190	0.657
Ovarian	0.151	0.819	0.587	0.652
Sarcoma	0.139	0.799	0.579	0.667

Entries in bold represent groups where the treatment effect is 0 (e.g. the treatment is ineffective). Thus, entries in bold are type I errors. Italicized entries appear where the treatment is effective, and thus indicate the power of the design.

Generally, type I error is controlled at 0.20 under the null scenario (the borrowing compensates for the multiple interim data reviews) and power is an increasing function of the expected sample size (power is higher in the higher accrual situation across treatment rate scenarios). In the alternative scenario there remains decently high probability of success even in the lower enrolling groups. When fewer groups are effective in truth, the scenarios “half” and “two” are harder to discern. Note in any particular trial there should be a mix of high and low enrolling cohorts, thus some cohorts may enroll closer to 10 subjects while other may only enroll five. This would produce a power value somewhere between the two tables.

Power is reduced and type I error is inflated when the truth is a mixture of effective and ineffective treatment effects across the cohorts. Generally power is a function of the sample size.

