8.4.1 Assumptions

Accrual – Two scenarios for the assumed two-year expected accrual are investigated: 1) 10 patients per group and 2) 5 patients per group. Note that these are averages, the actual number of available patients is simulated as a Poisson distribution with the specified mean. Also note that the group cap of 30 applies, and thus if the number of available patients in a group exceeds 30, only the first 30 available patients in that group will be enrolled in the study.

Dropouts – We assume no dropouts for the purpose of this simulation.

Control Rates – Table 1.1 shows the assumed control clinical benefit rates for each group.

Table 1.1 Assumed control rates

Tumor Type	Assumed Control Rate (R_g)
Lung NSC	0.45
Bladder	0.47
Breast	0.50
Colorectal	0.38
GIST	0.50
HNSCC	0.45
Ovarian	0.47
Sarcoma	0.40

Table 1.1 – Assumed control CBR values used in the simulations.

We consider four possible scenarios, or possible “truths” in the simulation. These consisted of a null scenario (where the treatment has no effect for any group), an alternative scenario (where the treatment is effective in all groups), a scenario where the treatment was effective in two of the groups, and a scenario where the treatment was effective in half of the groups.

Treatment Rates - The treatment rates for each scenario are shown in the Table 1.2. Values identical to the control are shown in bold, while values greater than the assumed control rate are italicized.

Table 1.2 Treatment rates

	Null	Alternative	Two	Half
Lung NSC	0.45	0.71	0.45	0.45
Bladder	0.47	0.73	0.47	0.47
Breast	0.50	0.75	0.50	0.50
Colorectal	0.38	0.65	0.38	0.38
GIST	0.50	0.75	0.50	0.75
HNSCC	0.45	0.71	0.45	0.71
Ovarian	0.47	0.73	0.73	0.73
Sarcoma	0.40	0.67	0.67	0.67

Simulation Details – For each scenario we simulated 1000 trials. For each interim within each trial, we ran 50,000 MCMC iterations after a 1,000 MCMC iteration burnin.

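### The alternative behind the sample size is said to include differing treatment effects, but the simulated one uses a common odds ratio of about 3 in all eight cohorts

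*Protocol*

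**What the plan says.** Protocol 10.8 rests the sample size on adequate power for the alternative of interest, citing Tables 4.2.1 and 4.2.2 of Appendix R. It describes that alternative as a treatment that works generally across groups, and says that it "incorporates variation in treatment effects to reflect the realistic expectation that treatment effects may differ by group". SAP 7 repeats the sentence.

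The scenarios are defined in Appendix R 4.1 ("Table 4.1.2 Treatment rates") and again in SAP 8.4.1 ("Table 1.2 Treatment rates"). There are four: Null, Alternative (effective in every group), Two (effective in two groups) and Half (effective in four). Protocol 10.4.2 sets the effect scale: it lets θ_g "be the mean log odds treatment effect", that is, the log odds in cohort g minus the log odds of the control rate R_g.

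The results text in Appendix R 4.2 makes two qualifications. For cohorts that accrue at different rates it says "This would produce a power value somewhere between the two tables". For cohorts with and without an effect it says "Power is reduced and type I error is inflated when the truth is a mixture of effective and ineffective treatment effects across the cohorts".

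**The concern.** Only the Alternative scenario is effective in all groups, so it is the one that Protocol 10.8 describes. Its treatment rates do differ between cohorts, from 0.65 to 0.75, but so do the control rates. What matters is whether θ_g differs. If it does not, the text credits the simulation with a feature it lacks.

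This bears on how the power is read. A common θ_g is a favourable case for a model that borrows across cohorts. The analysis model itself expects some variation between groups within a cluster (Appendix R 5, SAP 8.5). A reader of 10.8 would take the Alternative columns as already covering that variation. The documents in fact give no power for any effective cohort with a benefit smaller than an odds ratio of 3.

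**Working it through.** **1. Effects in the Alternative scenario.** Inputs are the control rates R in Protocol Table 4.1.1 and the Alternative rates π in Table 4.1.2 (SAP Tables 1.1 and 1.2). OR = [π/(1−π)] / [R/(1−R)]. The reverse check applies OR 3: π = 3o/(1+3o), where o = R/(1−R).

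| Cohort | R | π | OR | OR range from rounding of π | π if OR = 3 |
|---|---|---|---|---|---|
| Lung NSC | 0.45 | 0.71 | 2.99 | 2.92–3.07 | 0.7105 |
| Bladder | 0.47 | 0.73 | 3.05 | 2.97–3.13 | 0.7268 |
| Breast | 0.50 | 0.75 | 3.00 | 2.92–3.08 | 0.7500 |
| Colorectal | 0.38 | 0.65 | 3.03 | 2.96–3.10 | 0.6477 |
| GIST | 0.50 | 0.75 | 3.00 | 2.92–3.08 | 0.7500 |
| HNSCC | 0.45 | 0.71 | 2.99 | 2.92–3.07 | 0.7105 |
| Ovarian | 0.47 | 0.73 | 3.05 | 2.97–3.13 | 0.7268 |
| Sarcoma | 0.40 | 0.67 | 3.05 | 2.98–3.12 | 0.6667 |

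Example, Lung NSC: (0.71/0.29)/(0.45/0.55) = 2.448/0.818 = 2.99.

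Every entry in the last column rounds to the tabulated rate, and every rounding range contains 3.00. The SD of the eight log odds ratios is below 0.01, and the largest SD that rounding would permit is 0.033. The table is what a single θ = log 3 = 1.10 produces.

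**2. Reproducing the published power.** The Alternative columns average 7.358/8 = 0.920 at 10 per cohort and 6.498/8 = 0.812 at 5.

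The Appendix R model was recomputed by summing over all partitions of the eight cohorts (α = 2), with μ ~ N(0, variance 1.82) and τ² ~ IG(3, 0.5) integrated on a grid. Cohort sizes were Poisson with mean 10 or 5, cohorts needed at least 3 patients, and success was Pr(θ_g > 0) > 0.80. There were 10,000 trials per setting, and interim stopping was not modelled. Column means, recomputed against published:

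| Scenario | 10 per cohort | 5 per cohort |
|---|---|---|
| Alternative | 0.920 vs 0.920 | 0.803 vs 0.812 |
| Null | 0.145 vs 0.144 | 0.144 vs 0.144 |
| Half, OR-3 cohorts | 0.830 vs 0.835 | 0.670 vs 0.666 |
| Two, OR-3 cohorts | 0.760 vs 0.772 | 0.584 vs 0.583 |

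The largest gap anywhere is 0.015 (null cohorts in Half at 10 per cohort, 0.289 vs 0.304). The published power is therefore reproduced with a common effect.

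**3. Power when effects differ but all cohorts benefit.** The documents state no spread, so the SD is an assumption. The prior on τ² is used only to place it: its mean is 0.5/(3−1) = 0.25, the median of τ is 0.43, and the 5th to 95th percentiles of τ are 0.28 to 0.78. In the setting below, half the cohorts are at log 3 − SD and half at log 3 + SD.

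| SD of log OR | Average power, 10 per cohort | Fall (points) | Average power, 5 per cohort | Fall (points) |
|---|---|---|---|---|
| 0 | 0.920 | – | 0.803 | – |
| 0.25 | 0.904 | 1.6 | 0.794 | 0.9 |
| 0.43 | 0.869 | 5.1 | 0.771 | 3.2 |
| 0.50 | 0.850 | 7.0 | 0.758 | 4.5 |

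At SD 0.43 the two odds ratios are 3·exp(−0.43) = 1.95 and 3·exp(0.43) ≈ 4.62 (unrounded median τ 0.432). Power is 0.77 and 0.97 at 10 per cohort, averaging 0.87, and 0.65 and 0.89 at 5, averaging 0.77.

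**4. Sensitivity.** Reading 1.82 as an SD instead of a variance gives falls from 0.927 to 0.878 and from 0.816 to 0.781 at SD 0.43. A separate MCMC implementation (1,000 trials, no interim stopping) drew the log odds ratios from a normal distribution around log 3. It gave 0.922 at the tabulated rates, 0.898 at SD 0.3 and 0.854 at SD 0.5 with 10 per cohort, and 0.797, 0.774 and 0.741 with 5. At SD 0.5, about 1–2% of its cohorts had no benefit. Among those with benefit, power was 0.862 and 0.748.

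**The case against.** The strongest reply is that no published figure is wrong and that little is hidden. Control and treatment rates are both tabulated. The tables that 10.8 cites also carry Two and Half, where effects do differ, and the text warns of lower power there. Published power for OR-3 cohorts in those columns (0.758–0.852 at 10 per cohort, 0.579–0.688 at 5) lies below the SD 0.43 averages above. No numerical power target is stated, so 0.87 or 0.77 does not contradict a claim of adequate power. Enrollment closed in May 2015 with 106 patients, so nothing about accrual can change.

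Much of this stands. The fault is one of description, not of arithmetic in the tables, and it has no effect on conduct. The spread is assumed, and the prior's τ is a within-cluster SD applied here across all cohorts. At SD 0.25 the fall is about the Monte Carlo error of one published entry: with 1,000 trials, √(0.92·0.08/1000) ≈ 0.009. Most of the fall at larger SDs is simply that weaker true effects have less power.

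It does not rescue the clause. Two and Half have six and four null cohorts, so neither is a generally effective treatment, and their only non-null effect is still an odds ratio of 3. The warning concerns effective versus ineffective cohorts, not effective cohorts with unequal benefit. Risk differences do vary, from 0.25 to 0.27, but that is what a constant odds ratio gives on different control rates.

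**Conclusion.** The concern holds. The sample-size statements in Protocol 10.8 and SAP 7 attribute to the powered alternative a variation in effects that was not simulated. This follows from the documents' own tables and needs no assumption beyond their definition of θ_g.

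The consequence for power is moderate and conditional on the assumed spread. It is about 1 to 2 points of average power at SD 0.25, 3 to 5 at 0.43 and 5 to 7 at 0.5, each measured against the recomputed common-effect baseline. Cohorts with weaker benefit lose considerably more than the average. Interim stopping is not included in these figures. The published power remains valid for the case actually simulated.

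**What to change.** In Protocol 10.8 and SAP 7, replace the clause with a statement such as: *The Alternative-column power in Appendix R Tables 4.2.1 and 4.2.2 assumes an odds ratio of about 3 against R_g in every cohort; scenarios with unequal benefit among effective cohorts were not simulated.*

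If the sponsor prefers to keep the clause, the simulation has to support it. Add one scenario, at each accrual level, in which all cohorts benefit but θ_g differs. State the SD as an assumption (the prior median τ of 0.43 is one choice) and report success probability by true odds ratio. That is two further simulated settings.

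The rewording is one sentence per document and leaves sample size, priors, R_g and decision rules as they are. Protocol 12.1 requires a written, approved amendment for any protocol change. With enrollment closed, the correction could reasonably be made in the SAP and the clinical study report, and carried into the protocol only if it is amended for another reason. The one drawback for the sponsor is a plainer, less favourable reading of the power.

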## **11 Ethical considerations and administrative procedures**

### **11.1 Regulatory and ethical compliance**

This clinical study was designed, shall be implemented and reported in accordance with the International Conference on Harmonization (ICH) Harmonized Tripartite Guidelines for Good Clinical Practice (GCP), with applicable local regulations (including European Directive 2001/20/EC and US Code of Federal Regulations Title 21), and with the ethical principles laid down in the Declaration of Helsinki.

### **11.2 Responsibilities of the investigator and IRB/IEC/REB**

The protocol and the proposed informed consent form must be reviewed and approved by a properly constituted Institutional Review Board/Independent Ethics Committee/Research Ethics Board (IRB/IEC/REB) before study start. A signed and dated statement that the protocol and informed consent have been approved by the IRB/IEC/REB must be given to Novartis before study initiation. Prior to study start, the investigator is required to sign a protocol signature page confirming his/her agreement to conduct the study in accordance with these documents and all of the instructions and procedures found in this protocol and to give access to all relevant data and records to Novartis monitors, auditors, Novartis Clinical Quality Assurance representatives, designated agents of Novartis, IRBs/IECs/REBs and regulatory authorities as required.

### **11.3 Informed consent procedures**

Eligible patients may only be included in the study after providing written (witnessed, where required by law or regulation), IRB/IEC/REB-approved informed consent. Informed consent must be obtained before conducting any study-specific procedures (i.e. all of the procedures described in the protocol). The process of obtaining informed consent should be documented in the patient source documents. The date when a subject's Informed Consent was actually obtained will be captured in their eCRFs.

Novartis will provide investigators in a separate document with a proposed informed consent form (ICF) that is considered appropriate for this study and complies with the ICH and GCP guideline and regulatory requirements. Any changes to this ICF suggested by the investigator must be agreed to by Novartis before submission to the IRB/IEC/REB, and a copy of the approved version must be provided to the Novartis monitor after IRB/IEC approval.

Women of child bearing potential and fertile males should be informed that taking the study medication may involve unknown risks to the fetus if pregnancy were to occur during the study and agree that in order to participate in the study they must adhere to the contraception requirement for the duration of the study. Women of child bearing potential must agree to adhere to contraception requirement until at least 8 weeks after the final dose of study treatment. Fertile males must agree to adhere to contraception requirement until at least 21

days after the final dose of study treatment. If there is any question that the patient will not reliably comply, they should not be entered in the study.

#### **11.4 Discontinuation of the study**

Novartis reserves the right to discontinue this study under the conditions specified in the clinical study agreement. Specific conditions for terminating the study are outlined in [Section 4.2](#).

#### **11.5 Publication of study protocol and results**

Novartis assures that the key design elements of this protocol will be posted in a publicly accessible database such as clinicaltrials.gov. In addition, upon study completion and finalization of the study report the results of this study will be either submitted for publication and/or posted in a publicly accessible database of clinical study results.

#### **11.6 Study documentation, record keeping and retention of documents**

Each participating site will maintain appropriate medical and research records for this trial, in compliance with Section 4.9 of the ICH E6 GCP, and regulatory and institutional requirements for the protection of confidentiality of subjects. As part of participating in a Novartis-sponsored study, each site will permit authorized representatives of the sponsor(s) and regulatory agencies to examine (and when required by applicable law, to copy) clinical records for the purposes of quality assurance reviews, audits and evaluation of the study safety and progress.

Source data are all information, original records of clinical findings, observations, or other activities in a clinical trial necessary for the reconstruction and evaluation of the trial. Examples of these original documents and data records include, but are not limited to, hospital records, clinical and office charts, laboratory notes, memoranda, subjects' diaries or evaluation checklists, pharmacy dispensing records, recorded data from automated instruments, copies or transcriptions certified after verification as being accurate and complete, microfiches, photographic negatives, microfilm or magnetic media, x-rays, and subject files and records kept at the pharmacy, at the laboratories, and medico-technical departments involved in the clinical trial.

Data collection is the responsibility of the clinical trial staff at the site under the supervision of the site Principal Investigator. The study eCRF is the primary data collection instrument for the study. The investigator should ensure the accuracy, completeness, legibility, and timeliness of the data reported in the eCRFs and all other required reports. Data reported on the eCRF, that are derived from source documents, should be consistent with the source documents or the discrepancies should be explained. All data requested on the eCRF must be recorded. Any missing data must be explained. An audit trail will be maintained by the system.

The investigator/institution should maintain the trial documents as specified in Essential Documents for the Conduct of a Clinical Trial (ICH E6 Section 8) and as required by applicable regulations and/or guidelines. The investigator/institution should take measures to prevent accidental or premature destruction of these documents.

Essential documents (written and electronic) should be retained for a period of not less than fifteen (15) years from the completion of the Clinical Trial unless Sponsor provides written permission to dispose of them or, requires their retention for an additional period of time because of applicable laws, regulations and/or guidelines.

### **11.7 Confidentiality of study documents and patient records**

The investigator must ensure anonymity of the patients; patients must not be identified by names in any documents submitted to Novartis. Signed informed consent forms and patient enrollment log must be kept strictly confidential to enable patient identification at the site.

